Aim 3: To conduct preliminary analyses exploring whether emerging adults who receive the intervention demonstrate improvement in key symptom domains. Specifically, 40 youth will be randomized to either the integrated treatment or standard care. Primary outcomes will include substance abuse and PTSD. Secondary outcomes will include criminal justice involvement, adaptive functioning, and other mental health symptoms.

The results of the study will have a **significant impact on public health** by informing treatments for co-occurring SUD/PTSD among justice-involved transition age youth, a group at the highest risk for these problems. Demonstrating the efficacy of an integrated treatment approach will provide a valuable clinical tool for community-based therapists to employ in the context of existing evidence-based treatments. Further, should compelling indications of efficacy be found and safety and acceptability be established, these aims will position the research to advance to an appropriately powered randomized controlled trial.

A. SIGNIFICANCE

Prevalence and consequences of substance use problems among emerging adults. Transition age youth (i.e., emerging adults, ages 18-25) represent the age group with the **highest rates of initiation of substance use, increases in substance use, and progression of substance use into substance use disorders** (Chassin, Flora, & King, 2004; Delucchi, Matzger, & Weisner, 2008; SAMHSA, 2009). Substance use plays a significant role in many serious problems during this developmental period, including suicide (SAMHSA, 2010), automobile accidents (Hingson, Heeren, Winter, & Wechsler, 2005), and other lethal events. Emerging adults with SUDs also have increased rates of risky sexual behavior, increasing their chances of contracting HIV and other STDs (King, Nguyen, Kosterman, Bailey, & Hawkins, 2012). Further, SUDs significantly impede successful negotiation of important developmental tasks of this transitional age, leading to increased rates of unemployment and job instability and decreased college attendance (Bray et al., 2000; Mangione et al., 1999). Finally, emerging adults with SUDs represent a greatly underserved population, with a high likelihood of “slipping through the cracks” as they transition from child to adult substance use service providers ([name], Green, & Hoffman, 2009). **Thus, this group has a very high potential to present significant short- and long-term costs for individuals, families, and society.**

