Random Assignment occurs after the BL evaluation. A computerized urn randomization procedure (Stout et al., 1994) will balance patients on gender and submission of a positive sample for any illicit drug (i.e., cocaine, amphetamine, methamphetamine, opiate, benzodiazepine, or marijuana) at baseline, because positive samples at treatment initiation are related to poor outcomes (Preston et al., 1998; Silverman et al., 1998; Stitzer et al., 2007). Prior to randomizing participants, up to 10 pilot participants will complete a pilot study consent form and study procedures described for Group B below, through month 3 follow-up, for the purpose of monitoring staff on study procedures prior to the randomized trial.

Group A (Standard care [SC]; n=20) patients will receive SC at the substance use clinic where they are seeking treatment. This treatment approach typically consists of group therapy sessions, including daily planning, 12-Step treatment, relapse prevention, coping and life skills training, and AIDS education. Groups are led by recovering individuals, nurses, and masters level counselors. Very few individual sessions are provided at these clinics, and then only in cases of emergencies (e.g., suicidality). These clinics rarely conduct breathalyzers or urine testing for illicit drug use. Any such testing will occur as it normally would, and study procedures will not

impact standard care in any way. If the participant is not already enrolled in SC at a substance use clinic, they will be provided with referrals to clinics convenient to their home.

Study urine samples will be collected twice weekly. Patients will receive a \$5 payment (check or gift cards) for each of 20 urine/breath sample submissions during weeks 1-10. In addition, they will be asked to complete the NSSEP-SS and the CES-D to assess PTSD symptoms and depression weekly. If patients cease attending groups, they will still be encouraged to attend these brief meetings for sample monitoring. To maintain consistency with standard care in these clinics, results from toxicology screens will not be discussed with providers.

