Feasibility measures relevant to recruitment and dropout proportions will be examined with 95% confidence intervals used to estimate the proportion of emerging adults who agree to participate out of the number deemed eligible and to compare those who complete versus do not complete the intervention. Feasibility will be evaluated by examining therapist adherence using ratings of taped sessions as well as emerging adults' responses to qualitative interviews. Measures of safety will include repeat trauma exposure, suicidal ideation, and risky substance use behaviors. Patterns of safety indicators will be examined using frequency distributions and descriptive statistics. In addition, rates of these indicators will be compared across Group A and Group B to determine if there is any increased risk posed by the active treatment compared to treatment as usual. These data will be used to make any necessary protocol changes.

Aim 3: To conduct a preliminary analysis of the efficacy of the integrated protocol in improving symptoms among emerging adults.

Groups will be compared with respect to the primary outcome variables (substance use, PTSD symptoms) and secondary variables (delinquent behaviors, depression, adaptive functioning, HIV risk behaviors). An important issue preceding analyses is to identify baseline differences between groups despite random assignment. Differences between groups that may be related to outcome will be used as covariates or fixed factors, as appropriate. We will conduct intent-to-treat analyses, with all randomized patients and apply random regression models, also known as hierarchical linear models (HLM), to determine if patients improve differentially between groups over time (Raudenbush & Bryk, 2002). HLM is specifically designed for repeated measures designs with missing data, allowing for intra-subject serial correlation and unequal variance and covariance structures over time by incorporating available trend data for each individual with information on the group from which the subject is drawn. Maximum likelihood estimation enables analyses to be performed for the full trial without having to drop subjects with incomplete data, and both continuous and dichotomous variables can be analyzed. If data cannot be normalized, group by time effects will

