be assessed with HLM, coding patients as improved or not at each time point. The main analyses will focus on during treatment effects (baseline through follow-up) but long-term effects (baseline to 3-month post-treatment follow-up) will also be analyzed (see follow-up section).

The primary outcomes are substance use is longest duration of abstinence from illicit drug use and symptoms of PTSD (NSESP-SS), continuous variables that can be transformed if needed. The primary substance use outcome is longest duration of abstinence from substances (LDA), the main outcome variable in most CM trials and the variable most strongly associated with long-term abstinence (Higgins et al., 1994, 2000, 2003; Petry et al., 2005). Linear regression will evaluate group differences in LDA, with condition as the independent variable (along with any important covariates). If data cannot be normalized, nonparametric tests will be used. While LDA is the primary substance use outcome measure, it is affected by retention as missing samples break a string of abstinence (unless preceded and followed by negative samples, and an excused 'miss' is obtained due to documented illness, court appearances, etc. usually comprising <5% of missed samples). Proportion of negative samples, in contrast, is unaffected by missing samples. Thus, we will also analyze proportion of samples negative for substances as a secondary outcome using similar analyses.

Analyses will focus on the 10-week during treatment effects, but long-term effects will also be analyzed. These will involve logistic regressions to predict substance abstinence at the 3-month follow-up, with treatment group and any important baseline characteristics (e.g., baseline sample result) included as independent variables. HLM analyses for dichotomous measures will also be conducted to evaluate substance abstinence over time between treatments from baseline throughout the 3-month follow-up. Additional secondary drug use outcomes will investigate abstinence from all substances concurrently and from each of the other drugs independently. These analyses will parallel those outlined above.

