Effects of treatment on PTSD symptoms will be examined primarily using the weekly scores on the NSESP-SS. This is a continuous measure, with missing data likely. If no systematic differences in missing data are noted (the case in our prior studies), hierarchical linear models (HLM; Gibbons et al., 1993) using MIXREG (Hedeker, 1993) will analyze differences between groups over time. These analyses have advantages over repeated measures ANOVA as they estimate missing data via model parameter estimates and use real time, rather than scheduled time, of assessments. The model will include factors for group, time, and the interaction of group by time.

Secondary outcomes include delinquent behaviors (SRD), HIV risk behaviors (HRSB), adaptive functioning (SAS-SR), and depression (CES-D). Using the same HLM modeling described above, we will examine the impact of group, time, and group x time on each of these secondary outcomes to determine if the PE/CM treatment produces better outcomes than usual services.

Contingency Plan: If the intervention is not found to be feasible and/or produce symptom reduction, the candidate will work closely with mentors during Yr 5 to evaluate where positive outcomes are lacking and to refine the intervention using both quantitative and qualitative approaches. Assessment results will be evaluated to determine whether the intervention is equally effective across all areas targeted in treatment. If the intervention is found to be less effective in a specific area, modifications will be made to enhance the intervention in that area. Data will be examined to determine whether specific factors explain differential effects among participants. Input from participants will also be a critical source of information for improving the intervention.

PROTECTION OF HUMAN SUBJECTS

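### The mixed models appear to estimate a separate baseline mean in each randomised arm instead of using the baseline score in every case, which is valid but costs precision

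*Combined protocol and SAP*

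**What the plan says.** All of this is in the combined protocol and SAP, under Data Analysis Strategy, Aim 3, unless noted.

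- PTSD outcome: "Effects of treatment on PTSD symptoms will be examined primarily using the weekly scores on the NSESP-SS". The model: "The model will include factors for group, time, and the interaction of group by time".
- Secondary outcomes: "Using the same HLM modeling described above, we will examine the impact of group, time, and group x time on each of these secondary outcomes".
- Analysis window: "The main analyses will focus on during treatment effects (baseline through follow-up".
- Baseline covariates: "Differences between groups that may be related to outcome will be used as covariates or fixed factors, as appropriate".
- Size: "Specifically, 40 youth will be randomized to either the integrated treatment or standard care", 20 per arm. The Random Assignment section places randomisation after the baseline evaluation and balances on gender and baseline drug result only.

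No section names the baseline score as a standing covariate in these models, or sets the two arms' baseline means equal. The abstinence logistic regression mentions the baseline sample result as an example covariate, but that is a different analysis.

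**The concern.** Because baseline is measured before randomisation, the arms have equal expected baseline means. A model with a free group effect still spends information on estimating that difference, and then subtracts the noisy estimate when it forms the group-by-time term. A model that uses the known equality, or conditions on each participant's own baseline, gets a smaller standard error from the same data.

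With 20 per arm, the standard error of a chance baseline difference is √(2/20) = 0.32 SD. Neither balancing factor is PTSD or depression severity. Under the planned contrast, such a difference enters the group-by-time term as regression to the mean.

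The covariate rule does not secure the gain. It acts only on imbalances someone judges relevant after seeing the data, whereas the gain comes from the correlation between baseline and outcome, whether or not the arms differ. If baseline is also a response, the rule would put the same score on both sides of the model.

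**Working it through.** **Inputs.** From the documents: 20 per arm, baseline before randomisation, weekly scores over a 10-week treatment phase, other scales at 0, 3 and 6 months. The documents give no within-person correlation, SD, effect size or power, so there is no stated figure to reproduce and all correlations below are assumptions. Complete data and known covariance are also assumed. Variances are in units of the outcome variance.

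**Step 1: one baseline, one later visit.** With baseline-outcome correlation ρ, the free-group (change) contrast has variance proportional to 2(1−ρ) and the baseline-adjusted contrast to 1−ρ². The ratio is 2/(1+ρ):

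- ρ = 0.3: 1.40/0.91 = 1.54
- ρ = 0.5: 1.00/0.75 = 1.33
- ρ = 0.7: 0.60/0.51 = 1.18

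These apply only to a baseline-to-single-visit contrast.

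**Step 2: slope over several times.** Let V be the covariance matrix, t the vector of times and 1 a vector of ones. With equal arms, the variance of the slope difference with free baseline means, divided by that with a common baseline mean, is

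1 / {1 − (1′V⁻¹t)² / [(1′V⁻¹1)(t′V⁻¹t)]}.

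*Weeks 0 to 10, compound symmetry, ρ = 0.5.* V⁻¹ = 2(I − J/12), where J is the matrix of ones. Then 1′V⁻¹1 = 2(11 − 121/12) = 1.833, 1′V⁻¹t = 2(55 − 605/12) = 9.167 and t′V⁻¹t = 2(385 − 3025/12) = 265.83. The ratio is 1/(1 − 84.03/487.4) = 1.21.

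*Three equally spaced visits, same ρ.* With t coded 0, 1, 2 and V⁻¹ = 2(I − J/4), the terms are 1.5, 1.5 and 5.5. The ratio is 1/(1 − 2.25/8.25) = 1.38.

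Results for the other assumed structures (categorical time compares change to the last visit):

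| Design and structure | Linear time | Categorical time |
|---|---|---|
| Weekly, compound symmetry 0.3 / 0.5 / 0.7 | 1.44 / 1.21 / 1.09 | 1.54 / 1.33 / 1.18 |
| Weekly, AR(1) 0.8 / 0.9 / 0.95 | 1.93 / 1.50 / 1.25 | 1.81 / 1.48 / 1.25 |
| Weekly, random intercept and slope, uncorrelated | 1.01–1.12 | 1.05–1.24 |
| Weekly, the same with correlation −0.3 | 1.15–1.31 | 1.20–1.41 |
| 0/3/6 months, compound symmetry 0.3 / 0.5 / 0.7 | 1.66 / 1.38 / 1.19 | 1.54 / 1.33 / 1.18 |

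Every ratio exceeds 1. Interval width goes with the square root: a ratio of 1.1 is about 5% wider and 1.93 about 39% wider.

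**Step 3: would adding baseline as a covariate be enough?** Not if the test stays on group by time. Once baseline leaves the response, that term is the slope over post-baseline visits only. Under compound symmetry its variance is inversely proportional to the sum of squared deviations of time:

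- Weeks 0–10 give 110 and weeks 1–10 give 82.5, so the variance becomes 110/82.5 = 1.33 times the plan's.
- Months 0, 3, 6 give 18 and months 3, 6 give 4.5, so it becomes 18/4.5 = 4.0 times.

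Under AR(1) 0.8 and 0.9 the weekly figure is 0.86 to 0.87, so the loss is usual but not universal.

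**Step 4: covariate model with the adjusted difference read at week 10.** Under compound symmetry and linear time, its variance is (2/n)(1−ρ)[ρ + 1/10 + 4.5²/82.5] = (2/n)(1−ρ)(ρ + 0.345). The planned ten-week slope contrast has (2/n)(1−ρ)(100/110) = (2/n)(1−ρ)(0.909). The ratio (ρ + 0.345)/0.909 is 0.71, 0.93 and 1.15 at ρ = 0.3, 0.5 and 0.7.

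**The case against.** The strongest reply is that this is a Stage I pilot with preliminary efficacy analyses, no power claim, and a powered trial deferred. A group, time and group-by-time mixed model is standard and valid. That stands, and it limits the consequence to wider intervals.

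A reader might infer more than the documents support:

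- **That the primary PTSD analysis loses 2/(1+ρ), as if 35%, 25% or 15% of participants were discarded.** Those are single-visit results. The plan uses weekly scores, where the loss can be as little as about 1%.
- **That nothing handles chance imbalance.** The plan calls baseline differences an important issue before analysis and has a covariate rule. The rule is data-driven and does not secure the gain, but it exists.
- **That baseline is certainly a response.** The PTSD paragraph refers only to weekly scores, and the assessment table lists baseline and weekly measurement in separate columns. The window wording supports the inference without settling it. If baseline is left out altogether, the ratios above do not apply. At a single visit the loss would then be 1/(1−ρ²), or 1.33 at ρ = 0.5, so the baseline score is still worth using.
- **That every mixed-model outcome has a baseline value.** The SAS-SR, named for adaptive functioning, is absent from the assessment schedule, and the dichotomous abstinence models raise separate questions.

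**Conclusion.** The point holds as a matter of efficiency. The planned models appear to leave the baseline group difference free, and the covariate rule depends on observed imbalance, so precision available from data already collected is not secured.

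For weekly scores the slope variance is about 1.01 to 1.9 times that of a common-baseline model, and near 1.0 to 1.1 with uncorrelated random intercepts and slopes. For the 0/3/6-month scales it is about 1.2 to 1.7 times under compound symmetry. These ranges rest on assumed correlations, complete data and the inferred role of baseline. The documents cannot narrow them. The analysis is not invalid. Longest duration of abstinence, the other primary outcome, is analysed by linear regression and is not affected.

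**What to change.** In Data Analysis Strategy, Aim 3, state whether baseline is a response. Then prespecify one of the following, regardless of observed imbalance, for each continuous mixed-model outcome with a baseline measurement (NSESP-SS, CES-D, SRO, HRBS):

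- **(a)** Keep baseline in the response, constrain the arms to a common baseline mean, and keep the group-by-time test.
- **(b)** Model post-baseline scores with baseline as a covariate, and replace the group-by-time test with a named adjusted group difference, for example at end of treatment or averaged over post-baseline visits.

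Do not use the covariate form while still testing the post-baseline group-by-time slope, because that usually loses precision.

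The NSESP-SS baseline asks about the period since the event, while later assessments ask about the past month. It should not be the first point of a linear trend. Use (b), or (a) with baseline as its own categorical time point and the time of the group comparison named.

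The cost is wording and about one degree of freedom per model, with no new data. Option (b) also changes the contrast, and at week 10 with linear time it can be less precise than the plan under some structures (1.15 times the variance under compound symmetry at ρ = 0.7).

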1. RISKS TO THE SUBJECTS

A. Human Subjects Involvement and Characteristics

Human subjects are being recruited for the proposed study to participate in a clinical trial evaluating an integrated treatment for substance use and PTSD (SUD/PTSD) for transition age youth. Specifically, 40 youth will be recruited to participate in this study.

Inclusion criteria are: (a) 18-25 years old; (b) meets diagnostic criteria for a substance use disorder; (c) meets criteria for full or subthreshold PTSD; (d) currently able to provide a urine drug screen that is negative for cocaine and non-prescribed methadone or opiates in the past 60 days (since we are not able to test for methadone or determine whether a positive test for opiates is from a prescribed or non-prescribed source, we will rely on patient self-reports to make final decisions about the methadone and opiate results); and (e) speaks English. Exclusion criteria are: (a) significant cognitive impairment or serious uncontrolled psychiatric problems (other than PTSD); (b) in recovery from pathological gambling or current pathological gambling diagnosis and desiring to stop or reduce gambling (because of potential concerns of similarity of prize reinforcers and gambling even though no increases in gambling have been reported; and (c) in a current domestic violence relationship. Youth who meet eligibility requirements and consent to study participation will complete three assessment interviews over 6 months (i.e., at baseline, 3-, and 6-months post-baseline). Youth will be randomized to either the integrated SUD/PTSD treatment (plus treatment as usual) or to treatment as usual alone.

Targeted enrollment is based on estimates from past studies completed by the research mentors with transition age youth. There will be no restrictions with regard to gender, race, or ethnic background. Individuals will, however, be required to speak and understand English in order to participate in the study.

B. Sources of Material

Participant assessments will include self-report measures, interviews (semi-structured and qualitative), urine drug screens, and breathalyzer tests. Participants will be assessed at three time points (i.e., at baseline and 3-, and 6-months post-baseline). All assessments will be collected in person by the Research Assistant or PI. Assessments will be scheduled at a time and location convenient for the participant. At each occasion, participants will provide self-reports of substance use, symptoms of PTSD and depression, HIV risk behaviors, and adaptive functioning as well as a biological measurement of substance use. In addition, interviews will be used at the baseline measurement to assess demographics, other Axis I disorders, and PTSD diagnosis. Finally, youth in the PE-CM condition will participate in a qualitative interview at 3 and 6 months post-baseline focused on their perceptions of acceptability of the treatment and research protocols. All therapy sessions and research visits will be audiotaped to ensure therapist adherence to the treatment protocol and the Research Assistant's adherence to the research protocol. To compensate for their time, participants will be paid \$50 in giftcards for completing the initial assessments and \$100 in checks or giftcards for completing each of the follow-up assessments. Participants in the treatment as usual condition will be paid \$5 in checks or giftcards or small prizes per session for providing twice weekly urine and breathalyzer samples and completing brief self-report measures. Participants may also earn up to \$45 for referrals who complete an intake (\$15 each, up to 3 referrals).

C. Potential Risks

The risks that might be associated with this study include: 1) perceived coercion to participate; 2) potential embarrassment/distress due to sensitive assessment items; 3) potential distress if information obtained during the assessments were released to outside parties; and 4) potential distress due to participation in an exposure-based treatment for PTSD. As described next, several procedures will be used to protect against these risks.

